6. VIGILANCE AND MANAGEMENT OF ADVERSE EVENTS

6.1. DEFINITIONS

Vigilance	It is the monitoring of medicines, medical devices and other health products. It also consists of the prevention of the risk of adverse effects resulting from their use, whether this risk is potential or proven,
Adverse events (AEs)	Any harmful event occurring in a person who is a subject of research involving the human person, whether or not the event is related to the research or the product to which the research relates.
Intensity of Adverse Events (AEs)	
It will be scored according to the criteria chosen when the protocol was drafted
 
For any event not noted in the chosen classification, the rating will be as follows:
 
 1 = benign 2 = moderate 3 = severe 4 = life-threatening 5 = death
Adverse effects (AEs)	An adverse event occurring in a person who is a subject of research involving the human subject, where that event is related to the research or the product to which the research relates.
Serious adverse events (SAEs)/Events (SAEs)	
Any adverse effect/event that :
 
 * results in death, * is life-threatening, * results in temporary or permanent incapacity or disability, * requires or prolongs the patient's hospitalization, * causes a congenital or neonatal anomaly, * is medically important (the list of medically important effects/events is defined by the EMA).

Unexpected adverse events (AEs)	Any adverse reaction whose nature, severity or course is not consistent with the information about the products, procedures and methods used in the research.
New fact	Any new information that may lead to a reassessment of the risk/benefit balance of the research or the investigational product, to changes in the use of the investigational product, in the conduct of the research, or in the documentation of the research, or to the suspension or discontinuation or modification of the research protocol or similar research. For trials involving the first administration or use of a health product in persons without medical conditions: any serious adverse reaction.
Abuse	Intentional, persistent or sporadic excessive use of a drug that is accompanied by harmful physical or psychological reactions.
Overdose	Administration of an amount of drug, given at one time or cumulatively, that is above the maximum recommended dose according to the rules of compliance or use of the product. Clinical judgement should always be applied.
	(actual overdose: due to too much raw material / relative overdose: due to predisposing factors of the patient such as renal insufficiency, hypoalbuminemia...)
Misuse or off-label use	Situation where the product is intentionally used in a way that does not comply with the specifications for use of the product (e.g. different route of administration/posology or indication than listed in the reference document).
Medication error (ME)	Corresponds to any omission or unintentional, proven (or potential) performance of an act during the care process, in the circuit (from manufacture to administration) involving a product that may be the cause of a risk or an adverse event for the patient. The risk of error or potential error concerns situations where the error has not occurred, has been intercepted but could have occurred

6.2. LIST OF EXPECTED ARS

Within the framework of this protocol, the expected ARs are :

Concerning physical activity :

ARs related to physical activity are of the following types:

- musculoskeletal problems with more or less diffuse pain (limbs, neck, back, abdomen...), aches, contractures, cramps, musculoskeletal trauma including tendonitis...
- general/metabolic: hunger, malaise, shortness of breath, weight loss, weight gain.

Regarding the usual drug treatments for the disease:

The prescription of treatments is not modified by participation in the study. Given their diversity, it is not possible to propose an exhaustive list of expected effects.

The medicinal management of fibromyalgia and associated symptoms involves various pharmacological classes. The drugs are used within the framework of their MA and the expected AEs are listed in the current SPCs of the specialities concerned.

Medical devices can also be used (TENS, etc.) within the framework of their indications, their AEs are mentioned in the instructions for use.

6.3. *MANAGING ADVERSE EVENTS*

Collection of Evi/EI

In this minimal risk, minimal burden research, the protocol does not involve any changes to the usual management of patients.

The AEs related to the pathology studied (fibromyalgia), its treatment, the co-pathologies and their respective treatments, are neither to be entered in the vigilance part of the CRF, nor to be notified.

Under the responsibility of the investigator, as in the case of care, the notification of complications and AEs is part of the regulated systems: AEs related to drugs and DMs transmitted to the pharmacovigilance systems, materialovigilance, complications of procedures and examinations integrated into the risk management system of the institutions, etc...

The data concerning fibromyalgia and its evolution are traced in the dedicated part of the CRF.

In the framework of this study, which aims at the interest of a specific 6-month physical activity programme on the quality of life of the patients, only the **complications and AEs of the techniques having a potential impact on the protocol objective** will be collected and notified if a severity criterion exists:

- functional problems following the sessions that prevent the performance/continuation of physical activity
- malfunction of the activity tracking system

All developments and pregnancies that occur during the study will be traced and reported to the sponsor.

Notification of SAEs / EvIG

EvIGs and EIGs are notified to the appropriate vigilance circuits (a copy will be kept in the patient's clinical file).

In the context of this protocol, new developments, special situations, and complications that may impact the study objective are listed in the CRF and will be taken into account in the analyses planned according to the study schedule.

Only new developments and malfunctions in the tracking system should be reported to the promoter without delay after becoming aware of them so that corrective measures can be put in place.

Notification period to the promoter

The investigator is responsible for collecting and reporting to the appropriate monitoring system the various complications presented by patients.

It is the investigator's responsibility to record and report all AEs/SGEs, special situations or developments, as described above, whether expected or not, occurring during the entire study:

- from the date of signature of the randomisation -
and until the end of the study (i.e. M12)

6.4. MODALITIES AND DURATION OF FOLLOW-UP OF INDIVIDUALS FOLLOWING THE OCCURRENCE OF ADVERSE EVENTS

Any event, especially a serious one, must be followed up until recovery, consolidation or death (closed event).

Every pregnancy should be monitored at least until the birth of the child.

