In both arms of the study, the physical activity sessions are likely to cause more or less diffuse pain, aches, cramps, fatigue and discomfort. These symptoms are not specific to the study and are minimised by the supervision, which enables the absence of cardiac risk to be verified. Nevertheless, they may be felt as an increase in fibromyalgia pathology and experienced in a pejorative way by certain patients; this risk is minimised by the explanations provided within the framework of the research.

The constraints associated with attending the sessions and filling in the questionnaires were considered minimal, but could increase the anxiety of some participants.

Benefit/risk balance

The research manager qualifies the research in the first instance as **interventional research with minimal risks and constraints**, since :

- ✓ All procedures are performed in the usual way (*assessments, clinical examinations, interventions in physical activities*) and defined in the order of 12 April 2018 set by the Ministry.

The research does not focus on innovative or obsolete techniques or strategies.

Apart from the specialised physical activity offered to patients in the experimental group, the overall management of the patient will be identical to usual practice.

Consequently, the particular modalities of implementation in the research represent negligible constraints for the person who lends himself to the research. (Article R 1121-3 of the Public Health Code (CSP), decree n° 2006-477 of 26 April 2006).

The person in charge of the research will therefore, before any implementation of the research, submit the study protocol to the South-East III Committee for the Protection of Individuals (Comité de Protection des Personnes Sud-Est III) in accordance with Article L 1121-1 of the Version 3 of 02/10/2019

Page 9 on 33

Public Health Code (CSP) as they result from the laws n° 2004-806 of 9 August 2004 and n° 2006-450 of 18 April 2006 relating to public health policy, for a favourable opinion and confirmation of the research's qualification.

The bibliographical references are given in the annex to the document.

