4.2. GENERAL RESEARCH METHODOLOGY

The research has the following characteristics:

- Open study,
- Multicentric (CHD Vendée, CHU Nantes),
- Controlled,
- Of superiority,
- Randomised

Duration of inclusion: 18 months

Duration of participation: 12 months (*including 6 months of adapted physical activity depending on the randomisation arm*)

Duration of the research: 30 months

Randomisation arm :

- **Control group: Classic non-specific management in a common "multipathology" group, with activity trackers:**
 - One face-to-face session per week with the "Siel Bleu" association in the different sites of the Vendée and Loire-Atlantique.
- **Experimental group: Specific telephone coaching for fibromyalgia patients, with activity trackers:**
 - A one-hour face-to-face individual session conducted by the "Siel Bleu" association - Eight telephone coaching sessions in Physical Activity - Health :

- Four 30-minute sessions by the "Siel Bleu" association
- Four 30-minute sessions by physiotherapists from participating institutions

The nine sessions will be spread over 6 months.

Concerning the continuation of physical activity after the end of the experiment (i.e. after M6), the physical activity coaching service could be provided, if the patient so wishes and on his or her initiative, by a private physiotherapist or an adapted physical activity teacher from "Siel Bleu". Similarly, standard care is based on an existing activity currently offered by "Siel Bleu" and can therefore be integrated by the patient who so requests.

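### Section 6.3 ties collection of exercise problems to sessions, which read literally differs by arm and by period; the supervision statement in Section 1.2 does not fit the experimental arm

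*Combined protocol and SAP*

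**What the plan says.** Section 6.3 states that only the "complications and AEs of the techniques having a potential impact on the protocol objective" are collected, with notification where a severity criterion is met. Two items are listed: "functional problems following the sessions that prevent the performance/continuation of physical activity", and malfunction of the activity tracker. Events related to fibromyalgia itself are kept out of the vigilance part of the CRF. Later in Section 6.3, under the notification period, the investigator must "record and report all AEs/SGEs, special situations or developments, as described above, whether expected or not, occurring during the entire study", from randomisation to M12. The schedule in Section 4.5 marks adverse events between visits and at M6 and M12.

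Sections 4.2 and 4.3 describe what is delivered. Control patients attend a weekly group session with 40 minutes of interval training, and may do extra exercise through the association's website. Experimental patients have one individual hour, described as therapeutic education, and eight 30-minute telephone calls: "The nine sessions will be spread over 6 months". Participation lasts 12 months, "including 6 months of adapted physical activity depending on the randomisation arm". After M6, activity is at the patient's choice and initiative.

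Section 1.2 says: "In both arms of the study, the physical activity sessions are likely to cause more or less diffuse pain". It adds that these symptoms are "minimised by the supervision, which enables the absence of cardiac risk to be verified".

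**The concern.** The experimental programme uses coaching to prompt exercise that patients do by themselves between contacts. If the sessions are the delivered contacts, which is how Section 4.2 uses the word when it counts nine of them, a problem caused by that exercise does not follow a session and need not be recorded. The same holds for a control patient hurt during website exercise, and for self-directed exercise in either arm after M6.

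The item matters because it is the main study-level route for such problems. Section 1.2 accepts that exercise symptoms may be felt as a worsening of fibromyalgia, and Section 6.3 keeps fibromyalgia-related events out of the vigilance pages. Sites that read the word differently would apply different rules, and any by-arm description of these events would mix true differences with differences in capture. Separately, the benefit/risk text offers a safeguard for both arms that the design describes for only one.

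**Working it through.** **Sessions in the experimental arm (Section 4.2).** 1 face-to-face + 4 calls by the association + 4 calls by physiotherapists = 9, which agrees with the stated nine. Duration: 60 + 8 × 30 = 300 minutes. Exercise described within them: 0 minutes.

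**Sessions in the control arm (Sections 4.2 and 4.3).** Assuming 26 weeks and full attendance, 26 × 40 = 1,040 minutes of interval training from D0 to M6. Warm-up is not counted. The short periods of gentle stimulation within the 40 minutes are counted.

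**Share of the protocol's own exercise benchmark inside sessions.** Sections 2.2 and 4.3 set 240 minutes per month, built from four weeks of 60 minutes. The six-month total depends on the convention:
- six months: 6 × 240 = 1,440; control 1,040 / 1,440 = 72%
- 26 weeks: 26/4 × 240 = 1,560; control 1,040 / 1,560 = 67%
- experimental arm: 0% on either convention

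Over 12 months the control share is 1,040 / 2,880 = 36% or 1,040 / 3,120 = 33%, against 0%. These shares show how much of the recommended exercise the literal wording reaches. They do not measure how many events would be captured.

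**Time.** Recording covers 12 months and delivered activity covers 6, so 6/12 = 50% of the window has no study-delivered session in either arm. After M6 a patient may arrange a private physiotherapist or join the association's existing activity. Whether those count as the sessions is not stated.

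**The two readings side by side.**
- *Sessions are the delivered contacts.* Section 6.3 then leaves out exercise done between contacts and after M6, and Section 1.2 attributes diffuse pain in the experimental arm to an education hour and telephone calls.
- *Sessions are any bout of exercise.* Section 6.3 then covers both arms, but Section 1.2 says that symptoms from that exercise are limited by supervision. For the experimental arm, Section 4.3 describes only coaching calls informed by tracker data, which is remote review and not supervision of exercise.

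On either reading one of the two statements needs correcting.

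**Whether other text closes the gap.** The recording duty to M12 is for events as already described in Section 6.3, so it returns to the same list. The schedule in Section 4.5 sets when events are recorded, not which ones.

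**The case against.** The best defence is that the narrow reading is strained. Applied to the experimental arm, it would have the item cover activity-stopping problems caused by telephone calls, which is close to empty. Section 1.2 speaks of physical activity sessions in both arms, Section 6.2 lists exercise reactions with no session limit, and the parent sentence in Section 6.3 refers to the techniques, which Section 4.3 describes as including the activities proposed to experimental patients. Section 6.3 also says, without mentioning sessions, that complications bearing on the objective are listed in the CRF and taken into account in the analyses. The CRF is not among the documents, so its prompts cannot be checked. The coaching calls also give activity-stopping problems a route to staff.

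Much of this stands: the text is ambiguous, and sites may in practice record broadly. It does not remove the problem. The broad reading makes the supervision sentence untrue of the experimental arm as described. The CRF sentence repeats the category of complications without widening the listed item. Nothing says that problems mentioned during calls are passed to the CRF.

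A reader might go further and infer that harms will be under-counted in the experimental arm and the comparison tilted in its favour. The documents do not support that. Control website exercise and all exercise after M6 are affected too, actual recording practice is unknown, and exercise minutes are not a proxy for events.

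**Conclusion.** The point holds as a defect of wording with a practical consequence. Followed literally, Section 6.3 records exercise problems under a rule that differs between arms up to M6 and has no study-delivered session to attach to in either arm for the second half of the recording window. Followed broadly, it leaves Section 1.2 citing a safeguard that the experimental arm is not described as having. The coverage figures (67% to 72% of benchmark exercise in control and 0% in the experimental arm to M6) rest on 26 weekly sessions fully attended and on the choice of monthly or four-weekly counting. The contrast between arms does not depend on that choice.

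Neither the size nor the direction of any difference in recorded events can be derived. Two other inferences should be resisted. Serious events are not lost, because Section 6.3 sends them to the usual vigilance circuits in both arms. Nor does the trial fail an objective, because tolerability is not among those in Section 2. The FIQR comparison is unaffected.

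**What to change.** 1. In Section 6.3, replace the restriction to problems that follow sessions with: *during or after any physical activity, supervised or not, in either arm, from randomisation to M12*.
2. At the existing M6 and M12 visits, have the CETD evaluators, who under Section 4.1 are separate from those delivering the activity, ask one identical question in both arms: has a functional problem prevented or stopped physical activity since the last visit? Keep the existing severity criterion for notification. A checklist of all the reactions in Section 6.2 is not needed, and it would sit badly with that criterion and with the exclusion of fibromyalgia-related events.
3. In Section 1.2, limit the supervision sentence to the control group's face-to-face sessions. For the experimental arm, name the safeguards the protocol does describe: exclusion of patients with contraindications to physical activity (Section 3.3) and remote review of tracker data (Section 4.3).

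The cost is one phrase, one sentence, and at most 126 × 2 = 252 answers to a single question at visits that already take place. Slightly more events will be recorded. The change makes the rule the same for both arms but gives no power for harms: with 126/2 = 63 patients per arm, zero events would still leave a one-sided upper 95% limit of 1 − 0.05^(1/63) = 4.6%.

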4.5. STUDY SCHEDULE

TIMETABLE OF THE STUDY

Actions	J0 Inclusion visit	Between D0 and M6	M6	Between M6 and M12	M12
Patient information	X				
Collection of written consent	X				
Background	X				
Randomisation	X				
Clinical examination and questionnaires ¹	X		X		X
Encouragement to continue physical activity			X		
Physical activity with activity trackers		X	X	X ²	X ²
Analgesic treatments	X		X		X
Adverse events		X	X	X	X

¹EVA, DN4, HAD, WPI, SSS, impedance measurement, Tampa, FIQR, EQ-5D-5L

² Depending on the patient's choice

4.6. *IDENTIFICATION OF ALL SOURCE DATA NOT IN THE MEDICAL RECORD*

- Physical activity: practice at inclusion and type of activity
- Questionnaires: FIQR, DN4, Tampa, HAD, WPI, SSS, EQ-5D-5L
- EVA
- Physical activity during the study according to the randomisation arm (% success)
- Impedance measurement

4.7. *RULES FOR STOPPING A PERSON'S PARTICIPATION*

Criteria for premature termination of a person's participation in research

Any patient included in the protocol who no longer wishes to participate will be prematurely withdrawn from the study as soon as the request is made.

For the modalities and duration of the follow-up of the early leavers, see the statistical section.

- Withdrawal of patient consent at any time during the study, before publication of results.
Right to object to the use of the data at any time during the study, before publication of the results

Procedures for premature termination of a person's participation in research

For details of how to use the data of people who stopped the study prematurely, see the statistics section.

Criteria for stopping part or all of the research (excluding biostatistical considerations)

Part or all of the study may be stopped permanently or temporarily by decision of the ANSM, the CPP or the study sponsor.

A written confirmation will be sent to the coordinating investigator of the study (specifying the reasons for premature termination) and to the principal investigator of each centre if applicable.

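### Section 6.3 gives the sponsor prompt notice of tracker faults and new developments, but sets no sponsor recipient or deadline for other serious events linked to study exercise

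*Combined protocol and SAP*

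**What the plan says.** Section 6.3 of the combined protocol and SAP deals with events in three steps.

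- **Collection.** Events from fibromyalgia, its treatment and co-morbidities stay in the ordinary vigilance systems, described as "AEs related to drugs and DMs transmitted to the pharmacovigilance systems, materialovigilance, complications of procedures and examinations integrated into the risk management system" and so on (the list is left open). For the study itself, two items are in scope: "functional problems following the sessions that prevent the performance/continuation of physical activity", and malfunction of the activity tracker. Both "will be collected and notified if a severity criterion exists". A separate sentence adds: "All developments and pregnancies that occur during the study will be traced and reported to the sponsor".
- **Notification of serious events.** "EvIGs and EIGs are notified to the appropriate vigilance circuits", with a copy in the clinical file. Complications that may affect the study objective are listed in the CRF and "will be taken into account in the analyses planned according to the study schedule". Then comes the exclusive rule: "Only new developments and malfunctions in the tracking system should be reported to the promoter without delay after becoming aware of them". Its stated purpose is to allow corrective measures.
- **Notification period to the sponsor.** Under this heading the investigator reports complications to the appropriate monitoring system. The investigator also records and reports adverse events in the way already described, from randomisation to M12.

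Section 4.7 states who may act: "Part or all of the study may be stopped permanently or temporarily by decision of the ANSM, the CPP or the study sponsor".

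**The concern.** The sponsor is one of three bodies that can suspend or stop the study, and exercise is the intervention being compared. One would expect a serious event tied to that exercise to reach the sponsor at least as quickly as an equipment fault. The word that opens the fast-reporting rule excludes everything except new developments and tracker malfunctions. A single hospitalisation after exercise therefore reaches the sponsor promptly only if the site decides that it is a new development. A site seeing one isolated case may reasonably decide that it is not. A pattern across the Vendée sites and Nantes becomes visible only to someone who receives the individual cases.

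**Working it through.** No arithmetic applies, and no figure in the documents bears on the point. The check is to trace three kinds of event through sections 6.1 and 6.3.

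1. **A tracker malfunction.** The notification text sends it to the sponsor without delay. The collection text has it notified only when a severity criterion is met. That term is not defined in 6.3. Section 6.1 offers an intensity scale from benign to death and a list of seriousness criteria (death, threat to life, incapacity, hospitalisation, congenital anomaly, medical importance). Both describe harm to a person, and a sensor or data fault would not normally meet either. One text thus calls for immediate reporting where the other would normally call for none.

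2. **An event already recognised as changing the risk/benefit balance.** Section 6.1 defines a new fact as information that may prompt reassessment of that balance, or suspension or discontinuation. If the new developments of 6.3 are these new facts, the event goes to the sponsor without delay.

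3. **A hospitalisation after study exercise that the investigator regards as an isolated case.**
   - It meets a seriousness criterion in 6.1.
   - It is not automatically a new fact. Section 6.1 makes every serious adverse reaction a new fact only in trials of first administration or use of a health product in people without medical conditions, which this trial is not.
   - If it counts as a functional problem following a session, the collection text has it notified, without saying to whom or by when. Whether exercise done at home counts as a session is unclear. This matters in the experimental arm, which has one face-to-face session and eight telephone calls over six months (section 4.2).
   - The notification text sends it to the vigilance circuits and the clinical file. The sponsor is not named.
   - The exclusive rule then leaves it out of prompt reporting to the sponsor.
   - The paragraph on the notification period does not repair this. It gives a collection window and no deadline, names a monitoring system as recipient, and refers back to the rules above it.

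The sponsor has two other ways to learn of the third case. Data are entered in an eCRF (section 5.1), and a research associate visits each site regularly (section 7.4). Section 7.4 gives no visit interval and describes the visits as data quality control. Neither route has a time limit.

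**The case against.** The strongest reply is that the plan already has a fast route. New developments go to the sponsor without delay, and the definition in 6.1 includes information that may lead to suspension. An investigator who thinks a hospitalisation affects the risk/benefit balance must report it at once. This stands. A reader might infer that serious exercise-related events have no prompt route at all, and the text does not support that. The gap is confined to events not classed as new developments.

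A reader might also infer that such events reach the sponsor only through the CRF at the planned analyses. That goes too far. The schedule in section 4.5 marks adverse-event collection between visits as well as at M6 and M12, the CRF is electronic, and monitoring visits take place. The sponsor is CHD Vendée (section 7.3), so for Vendée patients the institution's own risk-management system may capture the event. The list of vigilance circuits is open-ended, so one cannot say that home exercise falls outside all of them. What remains is that none of these routes carries a time limit.

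Third, the plan deliberately scales vigilance to minimal-risk research, and section 7.4 classes the study as low or negligible risk. That supports light collection of expected, non-serious events. It does not explain giving an equipment fault a faster route than a serious event. Section 1.2 itself excepts the experimental arm's specialised activity when it says management is otherwise as usual. Whether regulation demands expedited reporting for this category cannot be settled from the documents, and the point does not rest on it.

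Finally, the two texts on tracker faults might serve different routes, since the collection text names no recipient, and the wording appears to be translated. That is possible. It makes the mismatch a matter for clarification rather than a proven contradiction.

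**Conclusion.** The concern holds in a limited form. For a serious event linked to study physical activity and not classed as a new development, section 6.3 states neither the sponsor as recipient nor a deadline, while its exclusive rule gives a tracker fault immediate reporting. Prompt sponsor awareness then depends on one site's classification. The severity condition on tracker malfunctions also sits badly with the without-delay rule.

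The size is qualitative. The documents give no rate of serious exercise-related events. The planned sample size and the tracker's monthly activity goal might tempt a reader to attach a number, but neither says how many events would be delayed or for how long.

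The conclusion assumes that new developments in 6.3 means the new fact of 6.1, and that promoter and sponsor are the same body. If the first assumption fails, the fast route is less clearly defined and the gap is wider.

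**What to change.** Reword the fast-reporting sentence in section 6.3. Serious events by the section 6.1 criteria, occurring during or attributed to study physical activity, in either arm and whether supervised or at home, should be reported to the sponsor without delay, alongside new developments and tracker malfunctions.

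Then reconcile sections 6.1 and 6.3:

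- use one term for new fact and new development;
- lift the severity condition from tracker malfunctions;
- state the recipient wherever 6.3 says an event is notified;
- put an actual period under the heading that announces one.

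The cost is a few sentences in one section and a few extra expedited reports. No study visit or assessment is added and the statistical analysis is unaffected.
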